10.9.2. Population PK/PD Dataset File Structure : ANGII

The PME compliant file structure is a space-delimited file with each row containing the following columns of information. Data from all treatments will be included.

Decision as to whether this will be required will be made following the planned interim analysis (for study Part 2 at approximately N=3 or approximately N=6).

Variable short name	Assessment description	Format	Unit	Valid Values / Format
C	Data Identifier	Integer	-	0
STUD	Protocol Number	Integer	-	204987
DRUG	Name of Drug	Integer	-	Maximum 10 characters (numeric or text). 2586881
SUBJ	Subject identifier in study	Integer	-	Maximum 10 characters (numeric or text). Different identifier for each subject
CENT	Study centre identifier	Integer	-	
LABL	Indicator field describing the type of assessment in that record	Integer	See footnotes	See footnotes
AMT	Dose of GSK2586881	Decimal	Mg	Amount of drug given = Total GSK2586881 dose (mg/kg) * WT. AMT=0 when LABL=0

Variable short name	Assessment description	Format	Unit	Valid Values / Format
				For dosing events: total dose of GSK2586881 taken For concentration events: 0
INF	Infusion Time	Decimal	h	Time during which total dose infused. (Time at end of infusion – Time of start infusion)
RATE	Rate of Infusion	Decimal	Mg/h	Rate of infusion (AMT/INF)
DGRP	Treatment Identifier	Decimal	-	DGRP=0 for placebo treatment DGRP=0.8 for 0.8 mg/kg treatment Dose of GSK2586881 (for all events)
PART	Study Part	Integer	-	1=Part 1 or 2=Part 2
PERIOD	Study Period	Integer	-	1=Period 1 or 2=Period 2
DAY	Study day	Integer	-	Maximum 10 characters (numeric or text) N= Day N, Actual Study Day
CTIM	Clock time of Dose or measurement	HH:MM:SS	-	
DATE	Date of record	DD/MM/YYYY		
TRFD	Actual time relative to FIRST dose	Decimal	Hours	When LABL=0 or 4, TIME =0 Hours since start of FIRST infusion (on Day 1). For pre-dose sample, TRFD is relative to FIRST dose
TRLD	Actual time relative to LAST dose	Decimal	Hours	When LABL=0 or 4, TIME=0 Hours since start of LAST dose/infusion. For pre-dose sample, TRLD is relative to previous dose For single dose studies TRLD = TRFD
TFLAG	Time Flag	Integer	-	At T0 and LABL=6, TFLAG=0 At T1 and LABL=6, TFLAG=1 At T2 and LABL=6, TFLAG=2 At T3 and LABL=6, TFLAG=3 At T4 and LABL=6, TFLAG=4 Otherwise if LABL=6, TFLAG=5 If LABL="0" or "4", TFLAG=6
BLII	AngII concentration record	Decimal		Baseline value (pre-dose value)
DV	AngII concentration record	Decimal		When LABL=6, observed AngII concentration at time specified by TRLD. When LABL=0 or 4, AngII=0
MDV	Missing data variable	Integer	-	Either '0' if DV value present or 1 if DV is non-quantifiable (NQ) value or LABL=0 or 4
MDV1	Missing data variable	Integer	-	'1' if LABL=0 or 4 "0" when LABL=6
TYPE	F-Flag	Integer	-	If MDV1='1' then TYPE ='0', If DV value present (but not NQ) TYPE= '1' If DV value NQTYPE = '2'
CMT	Compartment data	Integer	-	DOSE event: CMT=1, specifies the

Variable short name	Assessment description	Format	Unit	Valid Values / Format
	item			compartment into which DOSE is introduced. OBSERVATION event: CMT=3 for DV (ANGII) observation event.
AGE	Age	Decimal	Yrs	Integer. Age in years at time of screening rounded down to give age at last birthday.
WT	Weight	Decimal	Kg	Weight in kilograms at time of screening.
HT	Height	Decimal	Cm	Height in centimetres at time of screening.
SEX	Subject gender	Integer	-	Integer. One of the following - 1 = male 2 = female
ETHN	Subject ethnicity	Integer	-	Integer. Code as CRF
RACE	Subject race	Integer	-	Integer. Code as CRF
BMI	Body mass index	Decimal	kg/m ²	body mass index calculated as weight divided by height squared
EVID	Event Identification data item	Integer	-	Flag indicating whether LABL contains dosing admin info or drug concentration data. Valid values are - 1 – each dosing record for subject 0 – for all other records

Assessments captured in the LABL variable

Label	Description	Units
0	Dosing record for placebo	
4	Dosing records for 0.8 mg/Kg GSK2586881	
6	Observed record (concentration or ratio) at time specified by TRLD; excludes NA, IS and NR, includes non-quantifiable (NQ) data	

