2.3. Study Design

Overview of Study Design and Key Features	
	
The diagram illustrates the study design. It shows a vertical axis for 'Simulated Altitude [m]' with 0m at the bottom and 4000m at the top. A horizontal axis represents 'Time course of events'. The study begins at 0m, indicated by a vertical arrow pointing down. A dashed vertical line at approximately 1500m altitude represents the transition to 'Hypoxia'. The study then proceeds through several time points: T0 (dose at 0m), T1 (start hypoxia at 4000m), T2 (60 mins Echo at 4000m), T3 (10 mins exercise at 4000m, followed by Echo at 4000m), and T4 (return to 0m). The time axis is marked with 15 mins, 30 mins, 60 mins, T2 Echo, 10 mins exercise, T3 Echo, and 30 mins.

	
The above schematic represents Part 1 of the study. It is applicable also to Part 2 of the study, with the following modifications: simulated altitude will be 5000 m, and the T3 echo will be taken 2 minutes into the exercise challenge (rather than at the end of a 10-minute exercise challenge).

Design Features	
 Single centre Randomised Double-blind (sponsor open) Placebo-controlled Two-period crossover Study duration maximum 56 days
Dosing	
 Single IV dose in each study period

Overview of Study Design and Key Features	
Treatment Assignment	
 • Treatment A: Placebo • Treatment B: GSK2586881 0.8 mg/kg • Subjects will be randomised to one of two treatment sequences AB or BA
Interim Analysis	
 • Planned after approximately 10 subjects had completed treatment periods 1 and 2 (Part 1). The study may have been stopped if a reasonable change in PASP was not observed or if a review of safety data suggested a change in the benefit-risk profile. Following the interim, the decision was taken to continue the study with modifications to the protocol (Part 2). • In Part 2 an interim review is planned when approximately 3 subjects have completed treatment periods 1 and 2. A further review may take place when approximately 6 subjects have completed treatment periods 1 and 2, dependent on data observed in the earlier review. Subsequent interim reviews may take place, if deemed appropriate.

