10.1. Appendix 1: Time & Events

10.1.1. Protocol Defined Time & Events

10.1.1.1. Screening and Follow up

Procedure	Screening ¹ (up to 28 days prior to Treatment Period 1, Day 1)	Follow up (7-10 days post last dose)	Notes
Informed consent	X		
Inclusion and exclusion criteria	X		
Demography	X		
Full physical exam, including height and weight	X	X	Height and weight to be measured at screening only. Weight at screening will be used for dosing calculation.
Alcohol, Drugs of Abuse, Smoking test	X		
Medical history (includes substance usage [and family history of premature CV disease])	X		Substances: Drugs, Alcohol, tobacco
Past and current medical conditions [including cardiovascular medical history]	X		
Serum OR urine pregnancy test (WCBP)	X		
HIV, Hep B and Hep C screen	X		
Laboratory assessments (include liver chemistries)	X	X	Non Fasting
Immunogenicity		X	
12-lead ECG	X	X	Tripplicate ECG required at screening.
Vital signs	X	X	Tripplicate vital signs required at screening.
Spirometry	X		
Echocardiogram	X		
Concomitant Medication review	X	X	
Hypoxia chamber plus exercise	X		Part 1: Tolerance to 4000m for 10 mins followed by incremental exercise testing to determine maximum oxygen uptake (VO2max) and calculate 70% of VO2max (to be used for the exercise challenge during the Treatment Periods). Part 2: Tolerance to 5000m for 10 mins followed by incremental exercise testing to determine maximum oxygen uptake (VO2max) and calculate 50% of

Procedure	Screening ¹ (up to 28 days prior to Treatment Period 1, Day 1)	Follow up (7-10 days post last dose)	Notes
Pharmacogenetic sample (PGx)	X		VO2max (to be used for the exercise challenge during the Treatment Periods) Can be taken any time after consent has been signed. Only required once and is optional.
AE/SAE review	X	X	As per timings detailed in protocol Section 7.2.1.1

1. Screening assessments are allowed to be conducted on more than one day

10.1.1.2. Treatment Period 1 and 2

Procedure	Treatment Period 1 and 2 (Washout 3-14 days)										Notes
	Times relative to start of dosing				Hypoxic Challenge ~80 min (Times relative to entry to Chamber)						
	Pre-dose	0h	15 min	15-45 min	0-60 min	60 min	60-70 min	Immediately after exercise	On exit from chamber	After 30 min rest	
Randomisation	X										Treatment Period 1 only. Randomisation can occur up to the day before the first treatment period
Brief physical exam	X										
Vital signs	X			X				X ⁵			X
Immunogenicity	X										
12-lead ECG	X			X							X

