10.2. Appendix 2: Treatment States

10.2.1. Treatment States for AE Data

This study is a single dose two period crossover study. As such, AEs will be attributed to the treatment received within the relevant study period based on the dates and times of the AEs in relation to dosing date and time. This is as per IDSL dataset standards. This is detailed in the table below.

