10.9.5. Population PK/PD Dataset File Structure : Oxygen Saturation/PASP

The PME compliant file structure is a space-delimited file with each row containing the following columns of information. Data from all treatments will be included.

Decision as to whether this will be required will be made following the planned interim analysis (for study Part 2 at approximately N=3 or approximately N=6).

Variable short name	Assessment description	Format	Unit	Valid Values / Format
C	Data Identifier	Integer	-	0
STUD	Protocol Number	Integer	-	204987
DRUG	Name of Drug	Integer	-	Maximum 10 characters (numeric or text). 2586881
SUBJ	Subject identifier in study	Integer	-	Maximum 10 characters (numeric or text). Different identifier for each subject
CENT	Study centre identifier	Integer	-	
LABL	Indicator field describing the type of assessment in that record	Integer	See footnotes	See footnotes
AMT	Dose of GSK2586881	Decimal	Mg	Amount of drug given = Total GSK2586881 dose (mg/kg) * WT. AMT=0 when LABL=0 For dosing events: total dose of GSK2586881 taken For concentration events: 0
INF	Infusion Time	Decimal	h	Time during which total dose infused. (Time at end of infusion – Time of start infusion)
RATE	Rate of Infusion	Decimal	Mg/h	Rate of infusion (AMT/INF)

Variable short name	Assessment description	Format	Unit	Valid Values / Format
DGRP	Treatment Identifier	Decimal	-	DGRP=0 for placebo treatment treatment DGRP=0.8 for 0.8 mg/kg treatment Dose of GSK2586881 (for all events)
PART	Study Part	Integer	-	1=Part 1 or 2=Part 2
PERIOD	Study Period	Integer	-	1=Period 1 or 2=Period 2
DAY	Study day	Integer	-	Maximum 10 characters (numeric or text) N= Day N, Actual Study Day
CTIM	Clock time of Dose or measurement	HH:MM:SS	-	
DATE	Date of record	DD/MM/YYYY		
TRFD	Actual time relative to FIRST dose	Decimal	Hours	When LABL=1 or 4, TIME =0 Hours since start of FIRST infusion (on Day 1). For pre-dose sample, TRFD is relative to FIRST dose
TRLD	Actual time relative to LAST dose	Decimal	Hours	When LABL=0 or 4, TIME=0 Hours since start of LAST dose/infusion. For pre-dose sample, TRLD is relative to previous dose For single dose studies TRLD = TRFD
TFLAG	Time Flag	Integer	-	At T0 and LABL=6, TFLAG=0 At T1 and LABL=6, TFLAG=1 At T2 and LABL=6, TFLAG=2 At T3 and LABL=6, TFLAG=3 At T4 and LABL=6, TFLAG=4 Otherwise if LABL=6, TFLAG=5 If LABL="0" or "4", TFLAG=6
BLPASP	PASP	Decimal	mmHg	Baseline Value
PASP	PASP	Decimal	mmHg	When LABL=6, PASP at time specified by TRLD. When LABL=1, or 4, PASP=0

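### In the PK/PD dataset specifications (SAP 10.9.2 to 10.9.5), the sentence equating TRLD with TRFD contradicts both variables' definitions for Period 2 post-dose records

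*SAP*

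**What the plan says.** The design gives each subject two infusions, one placebo and one active, in sequence AB or BA (SAP 2.3: "Single IV dose in each study period"). The Appendix 1 schedule heads the treatment visits "Treatment Period 1 and 2 (Washout 3-14 days"). Section 10.2.1 classifies the trial in these words: "This study is a single dose two period crossover study".

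Sections 10.9.2 (Ang II), 10.9.3 (Ang 1-5), 10.9.4 (Ang 1-7) and 10.9.5 (oxygen saturation and PASP) specify NONMEM files that include all treatments. The placebo infusion is a dosing record with LABL=0 and the active infusion one with LABL=4. Observations have LABL=6 and are timed by TRLD.

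- TRFD is defined as "Hours since start of FIRST infusion (on Day 1"), and is set to zero when LABL is 0 or 4.
- TRLD is defined as "Hours since start of LAST dose/infusion", is also set to zero when LABL is 0 or 4, and the same cell adds "For single dose studies TRLD = TRFD".
- In 10.9.5 the TRFD row reads "When LABL=1 or 4, TIME =0". The PASP and oxygen saturation rows also use label 1. That section's label table lists only 0, 4 and 6, and its TRLD row uses 0 or 4.

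**The concern.** Because 10.2.1 calls the trial a single-dose study, the condition in the equality sentence is met on its face. Yet the file it governs has two infusions per subject, and one clock starts at the first infusion while the other restarts at the second. The sentence stands in the TRLD row, so it can be read as an instruction to fill TRLD from TRFD. TRLD is the time attached to every modelled observation. In sequence AB the active infusion is in Period 2, so the active-treatment peptide, PASP and saturation responses would be counted from the placebo infusion days earlier. In sequence BA the placebo responses would be counted from the active infusion. Any such error would therefore be tied to sequence.

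**Working it through.** **1. The SAP's own example of the two clocks.** Section 10.2.1.1 gives a Period 1 dose at 08:00 on 1 October 2016, a Period 2 dose at 08:30 on 8 October and an adverse event at 10:00 on 8 October. With the SAP's added minute:

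- since first dose: 7 d 2 h 0 min + 1 min = 7 d 2 h 1 min, as the SAP states;
- since period dose: 1 h 30 min + 1 min = 1 h 31 min, as the SAP states.

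Without the added minute these are 170.0 h and 1.5 h. The difference, 168.5 h, is the gap between the two doses. For adverse events, then, the SAP itself keeps the two clocks apart in Period 2.

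**2. The same arithmetic for TRFD and TRLD.** Let *g* be the gap between infusions and *t* the time since the infusion of the current period.

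- Period 1, post-dose: TRFD = *t*, TRLD = *t*. The equality holds.
- Period 2, post-dose: TRFD = *g* + *t*, TRLD = *t*. The equality fails by *g*.

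Inputs: *g* = 3 to 14 days = 72 to 336 h (Appendix 1 schedule, taking the washout as infusion to infusion). Nominal *t* is 0.25 h at T1. It is 0.5 h just before chamber entry, 0.5 + 1.0 = 1.5 h at T2, about 2.0 h at chamber exit and about 2.5 h at T4 (schedule, and the AUC windows in Table 6).

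| Period 2 sample | TRLD as defined | TRFD, *g* = 72 h | TRFD, *g* = 336 h |
|---|---|---|---|
| T1 | 0.25 h | 72.25 h | 336.25 h |
| Before chamber | 0.5 h | 72.5 h | 336.5 h |
| T2 | 1.5 h | 73.5 h | 337.5 h |
| Chamber exit | 2.0 h | 74.0 h | 338.0 h |
| T4 | 2.5 h | 74.5 h | 338.5 h |

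Filling TRLD from TRFD replaces the second column with the third or fourth. The error is additive and equals *g*.

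**3. The zero rule for TRFD.** At the Period 2 dosing record, the definition gives TRFD = *g*, that is 72 to 336 h. The rule for LABL 0 or 4 gives TRFD = 0. If that rule means that both clocks restart each period, the equality becomes true and TRLD is right, but TRFD is no longer time since the first infusion. Either way one statement in the specification is false.

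**4. The label code in 10.9.5.** Placebo dosing records carry LABL=0. The TRFD, PASP and saturation rules are written for LABL 1 or 4, so they reach active dosing records but no placebo ones. PASP and saturation on placebo dosing records are left without a stated value. TRLD, which uses 0 or 4, is not affected.

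**The case against.** The strongest reply is that the TRLD cell opens with the right definition, hours since the latest infusion, and that a programmer who follows it gets the right value. Period 2 records move only if the later sentence is allowed to override it. A benign reading also exists: both rows set time to zero at each dose, and elsewhere the SAP numbers days within each period (10.2.2.1). PERIOD, DATE and CTIM are in every file, so the correct time can be recovered. All of this stands, and it makes the mistiming a possibility and not a certainty. It does not make the text consistent, because the benign reading breaks TRFD's definition.

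Two further inferences are tempting and are not supported:

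- *The Period 2 pre-dose sample is mistimed.* It is not. The SAP times that sample's TRLD from the previous dose, so a value of days is what the variable means. TRFD for it runs from the first dose, which is the same infusion. Its role as baseline is carried separately, by the baseline column and TFLAG=0.
- *The population PK file (10.9.1) shares the fault.* That file excludes placebo, so each subject has one active infusion, and TRFD runs from the first active infusion. There the equality is correct, and it also settles the pre-dose sample.

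**Conclusion.** The equality sentence is wrong as written for 10.9.2 to 10.9.5. It fails for every Period 2 post-dose record. If applied as an assignment, it would shift those records by the gap between infusions, from about 0.25-2.5 h to about 72-338 h. The size rests on nominal sampling times and on the washout running infusion to infusion. The TRFD zero rule and label code 1 in 10.9.5 are separate inconsistencies in the same tables, and they do not depend on how the equality is read.

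A reader might express the shift as a multiple of the true time. That multiple depends on which sample is taken as divisor; the error itself is a constant added to each record. A reader might also infer that the trial's main results are at risk. The documents do not support this. The PASP model works on scheduled timepoints (7.2), and the modelling these files serve is conditional, exploratory and on a timeline independent of the RAP (8.4). Whether the files are needed at all is left to a decision after interim review.

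**What to change.** In 10.9.2 to 10.9.5:

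1. Delete the equality sentence, or limit it to Period 1 records. Limiting it has the small advantage that the Period 1 pre-dose sample, which has no previous infusion, still receives a value.
2. Keep TRLD as hours since the most recent infusion, with zero at each dosing record.
3. Set TRFD to zero only at the Period 1 dosing record, so that the Period 2 dosing record carries the time elapsed since the first infusion.
4. In 10.9.5, replace LABL=1 with LABL=0 in the TRFD, PASP and oxygen saturation rows, with the TRFD row also limited as in item 3.

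The convention for the Period 2 pre-dose sample and section 10.9.1 need no change. The cost is a few lines of specification text; dates, clock times and PERIOD are already in the files, so no new data are needed.

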10.9.3. Population PK/PD Dataset File Structure : ANG1-5

The PME compliant file structure is a space-delimited file with each row containing the following columns of information. Data from all treatments will be included.

Decision as to whether this will be required will be made following the planned interim analysis (for study Part 2 at approximately N=3 or approximately N=6).

Variable short name	Assessment description	Format	Unit	Valid Values / Format
C	Data Identifier	Integer	-	0
STUD	Protocol Number	Integer	-	204987

Variable short name	Assessment description	Format	Unit	Valid Values / Format
DRUG	Name of Drug	Integer	-	Maximum 10 characters (numeric or text). 2586881
SUBJ	Subject identifier in study	Integer	-	Maximum 10 characters (numeric or text). Different identifier for each subject
CENT	Study centre identifier	Integer	-	
LABL	Indicator field describing the type of assessment in that record	Integer	See footnotes	See footnotes
AMT	Dose of GSK2586881	Decimal	Mg	Amount of drug given = Total GSK2586881 dose (mg/kg) * WT. AMT=0 when LABL=0 For dosing events: total dose of GSK2586881 taken For concentration events: 0
INF	Infusion Time	Decimal	h	Time during which total dose infused. (Time at end of infusion – Time of start infusion)
RATE	Rate of Infusion	Decimal	Mg/h	Rate of infusion (AMT/INF)
DGRP	Treatment Identifier	Decimal	-	DGRP=0 for placebo treatment treatment DGRP=0.8 for 0.8 mg/kg treatment Dose of GSK2586881 (for all events)
PART	Study Part	Integer	-	1=Part 1 or 2=Part 2
PERIOD	Study Period	Integer	-	1=Period 1 or 2=Period 2
DAY	Study day	Integer	-	Maximum 10 characters (numeric or text) N= Day N, Actual Study Day
CTIM	Clock time of Dose or measurement	HH:MM:SS	-	
DATE	Date of record	DD/MM/YYYY		
TRFD	Actual time relative to FIRST dose	Decimal	Hours	When LABL=0 or 4, TIME =0 Hours since start of FIRST infusion (on Day 1). For pre-dose sample, TRFD is relative to FIRST dose
TRLD	Actual time relative to LAST dose	Decimal	Hours	When LABL=0 or 4, TIME=0 Hours since start of LAST dose/infusion. For pre-dose sample, TRLD is relative to previous dose For single dose studies TRLD = TRFD
TFLAG	Time Flag	Integer	-	At T0 and LABL=6, TFLAG=0 At T1 and LABL=6, TFLAG=1 At T2 and LABL=6, TFLAG=2 At T3 and LABL=6, TFLAG=3 At T4 and LABL=6, TFLAG=4 Otherwise if LABL=6, TFLAG=5

Variable short name	Assessment description	Format	Unit	Valid Values / Format
				If LABL="0" or "4", TFLAG=6
BL15	Ang1-5 concentration record	Decimal		Baseline value
DV	Angl1-5 concentration record	Decimal		When LABL=6, observed Ang1-5 concentration at time specified by TRLD. When LABL=0 or 4, Ang1-5=0
MDV	Missing data variable	Integer	-	Either '0' if DV value present or 1 if DV is non-quantifiable (NQ) value or LABL=0 or 4
MDV1	Missing data variable	Integer	-	'1' if LABL=0 or 4 "0" when LABL=6
TYPE	F-Flag	Integer	-	If MDV1='1' then TYPE ='0', If DV value present (but not NQ) TYPE= '1' If DV value NQTYPE = '2'
CMT	Compartment data item	Integer	-	DOSE event: CMT=1, specifies the compartment into which DOSE is introduced. OBSERVATION event CMT=5 for ANG1-5 observation event.
AGE	Age	Decimal	Yrs	Integer. Age in years at time of screening rounded down to give age at last birthday.
WT	Weight	Decimal	Kg	Weight in kilograms at time of screening.
HT	Height	Decimal	Cm	Height in centimetres at time of screening.
SEX	Subject gender	Integer	-	Integer. One of the following - 1 = male 2 = female
ETHN	Subject ethnicity	Integer	-	Integer. Code as CRF
RACE	Subject race	Integer	-	Integer. Code as CRF
BMI	Body mass index	Decimal	kg/m^2	body mass index calculated as weight divided by height squared
EVID	Event Identification data item	Integer	-	Flag indicating whether LABL contains dosing admin info or drug concentration data. Valid values are - 1 – each dosing record for subject 0 - for all other records

Assessments captured in the LABL variable

Label	Description	Units
0	Dosing record for placebo	
4	Dosing records for 0.8 mg/Kg GSK2586881	
6	Observed record (concentration or ratio) at time specified by TRLD; excludes NA, IS and NR, includes non-quantifiable (NQ) data	

10.9.4. Population PK/PD Dataset File Structure : ANG1-7

The PME compliant file structure is a space-delimited file with each row containing the following columns of information. Data from all treatments will be included.

Decision as to whether this will be required will be made following the planned interim analysis (for study Part 2 at approximately N=3 or approximately N=6).

Variable short name	Assessment description	Format	Unit	Valid Values / Format
C	Data Identifier	Integer	-	0
STUD	Protocol Number	Integer	-	204987
DRUG	Name of Drug	Integer	-	Maximum 10 characters (numeric or text). 2586881
SUBJ	Subject identifier in study	Integer	-	Maximum 10 characters (numeric or text). Different identifier for each subject
CENT	Study centre identifier	Integer	-	
LABL	Indicator field describing the type of assessment in that record	Integer	See footnotes	See footnotes
AMT	Dose of GSK2586881	Decimal	Mg	Amount of drug given = Total GSK2586881 dose (mg/kg) * WT. AMT=0 when LABL=0 For dosing events: total dose of GSK2586881 taken For concentration events: 0
INF	Infusion Time	Decimal	h	Time during which total dose infused. (Time at end of infusion – Time of start infusion)
RATE	Rate of Infusion	Decimal	Mg/h	Rate of infusion (AMT/INF)
DGRP	Treatment Identifier	Decimal	-	DGRP=0 for placebo treatment treatment DGRP=0.8 for 0.8 mg/kg treatment Dose of GSK2586881 (for all events)
PART	Study Part	Integer	-	1=Part 1 or 2=Part 2
PERIOD	Study Period	Integer	-	1=Period 1 or 2=Period 2
DAY	Study day	Integer	-	Maximum 10 characters (numeric or text) N= Day N, Actual Study Day
CTIM	Clock time of Dose or measurement	HH:MM:SS	-	
DATE	Date of record	DD/MM/YYYY		
TRFD	Actual time relative to FIRST dose	Decimal	Hours	When LABL=0 or 4, TIME =0 Hours since start of FIRST infusion (on Day 1). For pre-dose sample, TRFD is relative to FIRST dose
TRLD	Actual time relative to LAST dose	Decimal	Hours	When LABL=0 or 4, TIME=0 Hours since start of LAST dose/infusion. For pre-dose

Variable short name	Assessment description	Format	Unit	Valid Values / Format
				sample, TRLD is relative to previous dose For single dose studies TRLD = TRFD
TFLAG	Time Flag	Integer	-	At T0 and LABL=6, TFLAG=0 At T1 and LABL=6, TFLAG=1 At T2 and LABL=6, TFLAG=2 At T3 and LABL=6, TFLAG=3 At T4 and LABL=6, TFLAG=4 Otherwise if LABL=6, TFLAG=5 If LABL="0" or "4", TFLAG=6
BL17	Ang1-7 concentration record	Decimal		Baseline value
ANG1-7	Ang1-7 concentration record	Decimal		When LABL=6, observed Ang1-7 concentration at time specified by TRLD. When LABL=0 or 4, DV=0
MDV	Missing data variable	Integer	-	Either '0' if DV value present or 1 if DV is non-quantifiable (NQ) value or LABL=0 or 4
MDV1	Missing data variable	Integer	-	'1' if LABL=0 or 4 "0" when LABL=6
TYPE	F-Flag	Integer	-	If MDV1='1' then TYPE ='0', If ANG1-7 value present (but not NQ) TYPE= '1' If ANG1-7 value NQTYPE = '2'
CMT	Compartment data item	Integer	-	DOSE event: CMT=1, specifies the compartment into which DOSE is introduced. OBSERVATION event: CMT=4 for ANG1-7 observation event.
AGE	Age	Decimal	Yrs	Integer. Age in years at time of screening rounded down to give age at last birthday.
WT	Weight	Decimal	Kg	Weight in kilograms at time of screening.
HT	Height	Decimal	Cm	Height in centimetres at time of screening.
SEX	Subject gender	Integer	-	Integer. One of the following - 1 = male 2 = female
ETHN	Subject ethnicity	Integer	-	Integer. Code as CRF
RACE	Subject race	Integer	-	Integer. Code as CRF
BMI	Body mass index	Decimal	kg/m ²	body mass index calculated as weight divided by height squared
EVID	Event Identification data item	Integer	-	Flag indicating whether LABL contains dosing admin info or drug concentration data.

Variable short name	Assessment description	Format	Unit	Valid Values / Format
				Valid values are - 1 – each dosing record for subject 0 - for all other records

Assessments captured in the LABL variable

Label	Description	Units
0	Dosing record for placebo	
4	Dosing records for 0.8 mg/Kg GSK2586881	
6	Observed record (concentration or ratio) at time specified by TRLD; excludes NA, IS and NR, includes non-quantifiable (NQ) data	

